7.9 Safety

7.9.1 Adverse Events

All adverse events (AEs) recorded on the eCRF will be coded using the MedDRA dictionary Version 19.0 (or a later version if updated during the study) and classified as treatment-emergent AEs (TEAEs) as follows:

- TEAEs are events with start date on or after the date of first dose of study treatment and up to 14 days after date of last dose of study treatment or events with start date prior to the date of first dose of study treatment whose severity worsens on or after the date of first dose of study treatment.

Listings of Serious AEs (SAEs), AEs leading to discontinuation of study treatment, and AEs resulting in death will be produced by treatment group. Adjudicated cause of death will be described. AEs with an onset between signing of informed consent and study drug initiation, and those with onset more than 14 days after the last dose of study drug will be listed separately.

The number and percentage of subjects reporting each TEAE will be summarized by System Organ Class (SOC) and Preferred Term (PT) by treatment group and overall in the SAF population. Each subject will be counted only once within each PT or SOC and recording period. If a subject experiences more than one AE within a PT for the same recording period, only the AE with the strongest relationship or the worst severity, as appropriate, will be included in the summaries of relationship and severity. AEs with missing classifications regarding relationship to study drug and start date greater or equal to start of study drug will be considered as related to study drug. AEs that were reported to be at least possibly related to study drug will be considered as related to study drug.

Tables will be produced for the following TEAEs overall and by SOC and PT, preceded by an overview table:

- Any TEAE
- Most common TEAEs ($\geq 5\%$ in any treatment group)
- TEAEs by maximum severity
- TEAE related to study drug
- TEAEs related to study drug by maximum severity
- TEAE leading to study drug discontinuation
- TEAEs related to study drug and leading to study drug discontinuation
- TEAEs leading to study drug interruption
- Any TESAE (treatment-emergent serious AE)
- TESAE related to study drug
- TESAE leading to study drug discontinuation
- TESAEs related to study drug and leading to study drug discontinuation
- TESAEs leading to study drug interruption

- TESAE leading to death

No statistical comparisons of TEAEs between treatment groups will be performed.

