9 ADVERSE EVENTS

9.1 Adverse Events

The Investigator is to report all directly observed AEs and all AEs spontaneously reported by the subject using concise medical terminology. In addition, each subject will be questioned, in a non-directed manner about AEs at times specified in Table 1.

The AE reporting period for this trial begins upon signing of the informed consent form and ends at the final study visit (Visit 8).

All AEs that occur in subjects during the AE reporting period specified in the protocol, whether reported in response to a query, observed by site personnel, or reported spontaneously by the subject, must be recorded on the eCRF in the EDC system regardless of whether or not the event is considered medication related. Information to be collected and reported includes severity of the AE, relationship to study drug, duration of the AE, the treatment the subject is receiving at the time of the AE, and the outcome of the AE. The Investigator should attempt, if possible, to establish a diagnosis. For any AE which remains unresolved after completion of the study, the Investigator is responsible for following the AE to resolution or until a reasonable explanation for its persistence is found. In addition, any known untoward event that occurs subsequent to the adverse event reporting period that the Investigator assesses as possibly related to the investigational medication/product should also be reported as an adverse event.

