9.1.3 Pre-existing Condition Definition

In this trial, a pre-existing condition (i.e., a disorder present before the AE reporting period started and noted on the pretreatment medical history/physical examination form) should not be reported as an AE unless the condition worsens or episodes increase in frequency during the adverse event reporting period.

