9.1.5 Grading of Adverse Event Severity

If required on the AE CRFs, the Investigator will use the adjectives MILD, MODERATE, or SEVERE to describe the maximum intensity of the adverse event. For purposes of consistency, these intensity grades are defined as follows:

MILD	Does not interfere with subject's usual function
MODERATE	Interferes to some extent with subject's usual function
SEVERE	Interferes significantly with subject's usual function

Note the distinction between the gravity and the intensity of an AE. Severe is a measure of intensity; thus, a severe reaction is not necessarily a serious reaction. For example, a headache may be severe in intensity but would not be classified as serious unless it met one of the criteria for serious events listed above.

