11.3.1.2 Safety Analysis

Adverse Events

Safety data will be summarized in the Safety analysis set. All AEs will be coded using the Medical Dictionary for Regulatory Authorities (MedDRA). Treatment-emergent AEs are those with an onset after the first dose of study drug or any event already present that worsens in either intensity or frequency following exposure to the study treatment. Adverse events with an onset between signing of informed consent and study drug initiation, and those with an onset more than 14 days after the last dose of study drug will be listed separately. The incidence of treatment-emergent AEs, serious AEs, AEs resulting in study drug discontinuation, AEs at least possibly related to study drug, and fatal SAEs will be summarized by system organ class and AE preferred term in each treatment group. A summary of treatment-emergent AEs by preferred term and severity, using the worst reported severity grade for each event for a given subject, will be presented.

Clinical Laboratory

Descriptive statistics for laboratory parameter values, and for values of changes from baseline, by treatment group and visit, will be provided. The occurrence of significantly abnormal changes in laboratory values from baseline will be summarized by treatment group. Graphical representations may also be presented.

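### SAP 7.9.1 drops the protocol's frequency criterion for treatment-emergent adverse events without listing the change; the gap is confined to AE records that start before first dose

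*SAP*

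**What the plan says.** Protocol 11.3.1.2 treats an event as treatment-emergent if it starts after the first dose, and extends this to "any event already present that worsens in either intensity or frequency following exposure to the study treatment". SAP 7.9.1 has two clauses. The first takes events that start on or after first dose and up to 14 days after last dose. The second takes "events with start date prior to the date of first dose of study treatment whose severity worsens" on or after first dose. Frequency is not mentioned.

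The SAP restricts its AE summaries to events that meet this definition: "Tables will be produced for the following TEAEs overall and by SOC and PT, preceded by an overview table". Fourteen tables are then named, each limited to TEAEs or TESAEs. The SAP separately lists "AEs with an onset between signing of informed consent and study drug initiation".

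SAP Section 8, which sets out departures from the protocol, has one paragraph on safety events. It covers adjudicated events and fractures. The TEAE definition is not mentioned.

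**The concern.** The protocol gives two ways for an event already present at first dose to become treatment-emergent, and the SAP keeps one. A reader holding both documents cannot tell whether this was intended, because no reason is given and the change is not declared. SAP Section 8 otherwise records quite small changes, such as dropping one CK-18 assay and redefining the end date used for compliance.

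At stake is whether the TEAE counts in the report match the protocol's definition. Removing a criterion can only lower those counts. Safety is half of the stated study objective, and the TEAE tables are its main summary, so the definition should be the same in both documents or the difference should be stated.

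**Working it through.** No sample size, power or error rate is involved, so the check is a comparison of texts.

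**Does severity cover frequency?** No. Under Protocol 9.1.5 the investigator uses mild, moderate or severe "to describe the maximum intensity of the adverse event". That matches the protocol's intensity criterion and leaves frequency out.

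**Can records with a pre-dose start date exist?** Yes. Protocol 9.1 states: "The AE reporting period for this trial begins upon signing of the informed consent form". Screening lasts up to 42 days, and Protocol 6.2.2 lets consent precede that window.

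**How do the two definitions classify each kind of record?**

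| AE record | Protocol 11.3.1.2 | SAP 7.9.1 |
|---|---|---|
| A. Own start date on drug | TEAE | TEAE (first clause) |
| B. Pre-dose start, grade rises on drug | TEAE | TEAE (second clause) |
| C. Pre-dose start, same grade, more frequent episodes on drug, no new record | TEAE | Not a TEAE |
| D. Pre-dose start, no change on drug | Not a TEAE | Not a TEAE |

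Only row C differs.

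**What about conditions from the medical history?** Protocol 9.1.3 keeps a pre-existing condition out of AE reporting "unless the condition worsens or episodes increase in frequency during the adverse event reporting period". If its episodes increase on drug and the site dates the AE from that change, it falls in row A. If the site enters the original onset date, it falls in row C. The documents do not say which date to record, so the clearest row C cases are AEs that began between consent and first dose.

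**Where does a row C record appear?** Not in the overview or any of the 14 tables. It appears in the listing of AEs with onset between consent and first dose, if that is when it began. It also appears in the SAE, discontinuation or death listings if it qualifies, since SAP 7.9.1 does not limit those to TEAEs.

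**How many?** The documents give no rate of pre-dose AEs. As an illustration only, assume that 5–15% of subjects have such an AE and that 5–20% of those become more frequent on drug. With 380/4 = 95 subjects per arm:

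- low: 0.05 × 0.05 = 0.25%; 0.0025 × 95 = 0.2 subjects
- high: 0.15 × 0.20 = 3%; 0.03 × 95 = 2.9 subjects

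Under these assumptions the figures overstate the loss. They include subjects whose later episodes were entered as new records (row A), and subjects whose grade also rose (row B). Each subject is also counted once per preferred term, so any other on-drug record of the same term already puts the subject in the incidence table.

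**The case against.** A reader might infer that events which become more frequent on drug disappear from the TEAE tables as a class. The documents do not support that. An episode on drug with its own start date meets the SAP's first clause whatever happened before dosing, so the loss needs a single record opened before dosing and left to cover later episodes.

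A reader might also infer that a hypoglycemia signal would be lost. That does not follow either. Such episodes are discrete, and one reported on drug with its own date is a TEAE. Severe episodes are counted separately under SAP 7.9.7, as total events and as subjects, through 14 days after last dose.

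The strongest practical objection is that the protocol's criterion may not be workable. Protocol 9.1 states: "Information to be collected and reported includes severity of the AE, relationship to study drug, duration of the AE". Treatment at the time and outcome complete that list; frequency is not named. The eCRF is not available here, so this cannot be settled. If frequency was not collected, adding the word to the SAP changes nothing by itself. This objection stands, and the fix has to allow for it.

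The SAP also plans no statistical comparison of TEAEs between groups and applies the same rule to placebo and active arms. That limits the consequence. It does not remove the contradiction between the documents or the silence of Section 8.

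**Conclusion.** The inconsistency is real and undeclared, and its consequence is minor. For row C records the SAP contradicts the protocol, and the effect runs one way, towards fewer TEAEs. The number of subjects cannot be derived from the documents; it is probably very small and may be zero. That judgment assumes that most on-drug recurrences are entered as new records, which the documents neither require nor rule out. The documents give no ground for claiming that incidence by dose is materially understated. No efficacy result or hypothesis test is touched.

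**What to change.** In SAP 7.9.1, change the second clause so that it reads *whose severity or frequency worsens*, and state how increased frequency is identified. Either of two rules would do: blinded review, before final database lock, of AEs with onset between consent and first dose; or a new AE record dated at the change.

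If frequency data were not collected, say so in the SAP and list the narrower definition, with that reason, in Section 8.

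If an upper limit of 14 days after last dose is wanted on the worsening clause, add it as a separate clarification. It would be consistent with the safety window in SAP 5.3, but the protocol's worsening clause contains no such limit, so it should not be presented as protocol wording.

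The cost is one phrase in the SAP and a small manual review, or one added sentence in Section 8.

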7.9.2 Laboratory Evaluations

Values for the following safety laboratory tests (hematology, serum chemistry, and urinalysis) will be listed and summarized by treatment group and visit.

Hematology	Serum Chemistry	Urinalysis
Hemoglobin	Albumin*	Bilirubin
Hematocrit	Alkaline phosphatase (ALP)*	Blood
Platelets, RBC with indices	Alanine aminotransferase (ALT)*	Glucose
WBC with differential	Aspartate Aminotransferase (AST)*	Ketones
HbA1c*	Blood Urea Nitrogen (BUN)	pH
INR*	Bicarbonate	Creatinine
PT*	Calcium	Protein
	Chloride	Specific gravity
	Creatinine	Microscopic exam (if blood or protein positive)
	Fasting plasma glucose (FPG)*	
	Fasting insulin*	
	Free fatty acid (FFA)*	
	Lactate dehydrogenase (LDH)	
	Phosphorus	
	Potassium	
	Sodium	
	Gamma-Glutamyl transpeptidase (GGT)*	
	Total Bilirubin*	
	Total protein	
	Uric acid	
	Cholesterol (total, HDL, LDL, VLDL)*	
	Triglycerides*	

*Also considered an efficacy parameter.

All laboratory data will be reported in International System of Units (SI).

For analysis purposes, values preceded by a “<” or a “>” sign (i.e., those below or above the limits of quantification) will be considered equal to 0.5 × the lower limit or 1.5 × the upper limit of quantification, respectively. The proportion of subjects with values below the lower limit and above the upper limits of quantification will be provided among the summary statistics.

Laboratory evaluations measured on a continuous scale will be summarized by visit using standard descriptive statistics for the SAF population. Changes from baseline will also be summarized. Summaries will be presented for log-transformed values of ALT, AST, ALP, and GGT, in addition to summaries of non-transformed values. For analysis by visit, analysis windowing as described in Section 6.1 will be used for each scheduled visit such that unscheduled visits will also be considered. For each laboratory analyte, the baseline value will be defined as last scheduled or unscheduled value collected prior to the first dose of treatment.

For hematology and serum chemistry, shift tables presenting movement in and out of reference range from baseline to each scheduled post-baseline visit will be provided for each treatment group. An additional shift table will be produced for ALT where the upper normal limit is defined as 19 U/L for women and 30 U/L for men. Corresponding shift tables (normal vs. high /

normal vs. abnormal) will be produced for urinalysis. Additional tables will summarize the occurrence at each visit of clinically significant abnormal changes from baseline by treatment group for the following analytes: ALT, AST, GGT, and alkaline phosphatase with abnormal change defined as ratio to baseline ≥ 5 , and total bilirubin with abnormal change defined as ratio to baseline ≥ 2 .

Mean change from baseline with standard error bars will be plotted for each treatment group by visit for select laboratory parameters (hemoglobin, ALT, ALP, AST, Creatinine, total bilirubin) for the SAF population.

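### Half-limit substitution flags any bilirubin that goes from unquantifiable at baseline to quantifiable as clinically significant, and the same rule can give impossible urine values

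*SAP*

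**What the plan says.** SAP 7.9.2 covers all three laboratory panels: "Values for the following safety laboratory tests (hematology, serum chemistry, and urinalysis) will be listed and summarized by treatment group and visit". Its urinalysis column includes pH and "Specific gravity".

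The substitution rule opens "For analysis purposes, values preceded by a" less-than or greater-than sign and says that such values "will be considered equal to 0.5 × the lower limit or 1.5 × the upper limit of quantification". It exempts no analyte and no use.

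Later in the section: "Additional tables will summarize the occurrence at each visit of clinically significant abnormal changes from baseline by treatment group". Two thresholds follow:

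- "ALT, AST, GGT, and alkaline phosphatase with abnormal change defined as ratio to baseline ≥ 5"
- "total bilirubin with abnormal change defined as ratio to baseline ≥ 2"

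The denominator is a single measurement: "the baseline value will be defined as last scheduled or unscheduled value collected prior to the first dose of treatment". There is no separate provision for a baseline below the limit of quantification.

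The section also reports the share of subjects outside each limit, gives reference-range shift tables for hematology and chemistry, and gives normal-versus-high or normal-versus-abnormal shift tables for urinalysis. Laboratory tests on a continuous scale get standard descriptive statistics and changes from baseline.

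**The concern.** The substitution constant (0.5) and the bilirubin threshold (2) are reciprocals, and the threshold is inclusive. Crossing the limit of quantification is therefore enough to be counted as a clinically significant change, whatever happened in the subject. The bilirubin table is part of the trial's liver-safety reporting, and a reader of that table cannot tell a flag produced by the substitution from a measured doubling.

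Multiplying a limit by 0.5 or 1.5 also makes no sense for a quantity confined to a narrow band away from zero. Urine specific gravity and pH are of that kind. If signed results for them enter the numeric summaries, the means, SDs, extremes and mean changes will contain values that no urine sample can have.

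**Working it through.** The plan gives no figure of its own here to reproduce. The check is algebra on its constants.

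**Inputs from SAP 7.9.2.** Below-limit result = 0.5L; above-limit result = 1.5U; bilirubin flag at ratio ≥ 2; ALT, AST, GGT and ALP flag at ratio ≥ 5; baseline = last pre-dose value.

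**Not in the documents.** L and U for any analyte, and the frequency of signed results. Limits used below are assumptions.

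**Bilirubin.** With a below-limit baseline and a later quantifiable value y ≥ L:

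ratio = y / (0.5L) ≥ L / (0.5L) = 2.0

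| Later value | Ratio under the SAP rule | Flagged? | Ratio if baseline set to L | Flagged? |
|---|---|---|---|---|
| L | 2.0 | yes | 1.0 | no |
| 1.1L | 2.2 | yes | 1.1 | no |
| 1.5L | 3.0 | yes | 1.5 | no |
| 2L | 4.0 | yes | 2.0 | yes |

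L cancels, so assumed limits of 0.1, 0.15, 0.2 and 0.3 mg/dL all give exactly 2.0 at y = L. The true change behind such a flag can be very small. For y = L, a true baseline of 0.99L is a 1.01-fold rise, 0.9L is 1.11-fold and 0.75L is 1.33-fold. Only a true baseline of 0.5L or lower is a real doubling.

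**Rounding.** At y = L the ratio sits exactly on the threshold, and results are reported in SI units. With L = 0.1 mg/dL and a conversion factor of 17.104, L is 1.71 and 0.5L is 0.86 after rounding to two decimals, and 1.71/0.86 = 1.99, which is not flagged. This affects only values at the limit itself.

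**Other liver analytes.** Ratio ≥ 5 needs y ≥ 5 × 0.5L = 2.5L, so crossing the limit does not trigger those flags by itself.

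**Urine, with assumed limits.**

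- Specific gravity above 1.030: 1.5 × 1.030 = 1.545. Any U of at least 1.000 gives at least 1.5.
- Specific gravity below 1.005: 0.5 × 1.005 = 0.5025, about half the density of water.
- pH above 8.5: 1.5 × 8.5 = 12.75. This lies on the 0–14 scale (14 is passed only if U exceeds 14/1.5 = 9.33) but is not a possible urine pH.

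To illustrate the size, assume 90 subjects, 89 of them with mean 1.020 and SD 0.007, and one set to 1.545. The mean moves by 0.525/90 = 0.0058. The variance is (88 × 0.007² + 0.525² × 89/90)/89 = (0.0043 + 0.2726)/89 = 0.00311, so the SD is about 0.056, eight times the assumed 0.007. The median barely moves.

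**The case against.** The strongest reply is that the problem may never arise. The documents do not say that any bilirubin will be reported below a limit, or that specific gravity or pH will carry a sign or be treated as continuous. This stands: the count of affected subjects is unknown and could be zero, and the urine point is conditional.

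The plan also has safeguards. It reports the shares outside the limits and lists the data. The chemistry shift tables would show no move to high when a bilirubin rises within the reference range. The urine shift tables would usually classify an above-limit result correctly. Medians and quartiles are reported beside the means. These help a careful reader, but none of them removes the flag or corrects a substituted mean.

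Three stronger readings are tempting, and the documents do not support them:

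- **Several false flags per arm, rivalling the real ones.** A reader might infer this, but the documents give no frequency of below-limit baselines and no expected number of doublings.
- **A blurred comparison between arms.** The flag table is descriptive, 7.9.2 plans no test of it, and the rule is identical in every arm. No differential effect is shown.
- **A missing upper-limit-of-normal condition as an error.** Protocol 6.5 also uses a purely baseline-relative bilirubin criterion. Adding such a condition would redefine the sponsor's flag and is not needed to remove the artefact.

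**Conclusion.** The point holds as an internal clash between two rules in SAP 7.9.2. Followed as written, the plan flags every subject whose bilirubin is unquantifiable at baseline and quantifiable later, apart from rounding at the limit, whether or not anything changed. This needs no assumption about the assay. How many subjects it touches cannot be derived from the documents.

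The urine part rests on two conditions: that signed specific gravity or pH results occur, and that they are summarised as continuous. If both hold, the damage is confined to means, SDs, extremes and mean changes.

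This is a minor defect in descriptive safety output. It does not touch the primary endpoint.

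**What to change.** Add two sentences to SAP 7.9.2:

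1. For the ratio-to-baseline flags only, a baseline reported as below L is set to L. The half-limit value may stay in the other summaries.
2. For urine specific gravity and pH, results with a sign are set to the reported limit itself.

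Crossing the limit then no longer triggers the bilirubin flag by itself. Because the true baseline lies below L, any value of 2L or more is a real doubling.

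The cost is some sensitivity at very low values. A subject with a below-limit baseline needs at least 2L for the bilirubin flag, so a real doubling that ends between L and 2L is missed. At an assumed L of 0.1 to 0.3 mg/dL, 2L is 0.2 to 0.6 mg/dL; for scale, the bilirubin entry limit in the protocol is 1.8 mg/dL. For the enzymes the requirement moves from 2.5L to 5L. The programming change is small. It should be settled before unblinding for the final analysis, because removing liver flags afterwards would look selective.

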6.5 Liver Function Tests

If subjects demonstrate an increase in AST, ALT or total bilirubin (TB) greater than 2 times their baseline values (mean of Screening & Visit 1), there should be repeat tests of transaminases (AST and ALT), bilirubin, and physical exam performed within 48-72 hours. If the levels then decrease, the subjects will be under close observation (repeat testing 2-3x weekly) until the levels return toward the individual's baseline values. Should these levels continue to be elevated, the drug should be discontinued.

Subjects should be discontinued for elevations of transaminases (AST or ALT) or TB above baseline associated with symptoms of right upper quadrant abdominal pain, fatigue, anorexia, nausea or vomiting, or eosinophilia. Subjects should be discontinued for persistent (> 1 month) increases of AST and ALT and/or TB > 2 times baseline.

Subjects may be rechallenged with study drug and closely monitored with repeat testing at least weekly. Re-elevation of values after re-challenge necessitate permanent discontinuation of study drug (but continuation of study visits).

If a new concomitant medication with known hepatotoxicity is started and liver function tests rise to meet the above criteria, the known hepatotoxin should be discontinued (replaced) if possible and liver function tests be followed in the same manner as outlined above. If liver function tests remain elevated or increase further, then the study drug should be discontinued (and subjects should continue with the study visits).

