6 DATA HANDLING

6.1 Time points and Visit Windows

Study Day 1

Study day 1 is defined as the date of the first dose or the date of randomization for subjects who were not administered any dose of study drug.

Study Day

Study days after study day 1 are calculated as (assessment date – study day 1 date) + 1. Study days prior to study day 1 are calculated as (assessment date – study day 1 date). The day prior to study day 1 is study day -1, there is no study day 0.

Scheduled and Unscheduled Visits

For the purpose of statistical analysis, the nominal visit designations as assigned by the investigator will be used. Unscheduled visits will be programmatically assigned to a nominal visit designation according to the following definition of visit windows.

Definition of visit windows to assign unscheduled visits to nominal visit designations

Nominal Visit	Target Day (Study Day)	Parameter measured at all visits	Parameter measured at all visits except Visit 8	Parameter measured at all visits except Visits 2, 3, and 8	Parameter measured at Visits 1, 5, 7 and 8	Parameter measured at Visits 1, 5, and 7	Parameter measured at Visits 1 and 7
1 Baseline	1	≤1	≤1	≤1	≤1	≤1	≤1
2 Month 1	30	2-45	2-45	--	--	--	--
3 Month 2	60	46-75	46-75	--	--	--	--

Statistical Analysis Plan

Version: Final 1.5

Date of Issue: 16-May-2019

Cirius Protocol No. MSDC-0602K-C009NASH

4 Month 3	90	76-135	76-135	2-135	--	--	--
5 Month 6	180	136-225	136-225	136-225	2-270	2-270	--
6 Month 9	270	226-315	226-315	226-315	--	--	--
7 Month 12	360	316-367	≥316	≥316	271-367	≥271	≥271
8 Follow-up	374	≥368	--	--	≥368	--	--

For all populations, multiple visits for a given parameter with the same nominal visit designation will be dealt with as follows:

- If both scheduled and unscheduled visit data are available, the scheduled visit data will be used for analysis with the exception of baseline, where the baseline value will be defined as the last scheduled or unscheduled value collected on or prior to the date of the first dose of treatment (or randomization for subjects who were not administered any dose of study drug).
- If multiple unscheduled visits occur within the same visit window and no data from a scheduled visit is available for the corresponding nominal visit designation, then the unscheduled visit closest to the corresponding target day will be used in the analysis. If there is a tie, the later unscheduled visit will be used in the analysis.

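### The SAP's ALT/AST abnormality table starts at 5 times baseline, so no planned table counts, by arm, rises above 2 and below 5 times, a band the protocol acts on

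*SAP*

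**What the plan says.** **Reporting rule (SAP 7.9.2).** The SAP tabulates, at each visit and by treatment group, what it labels clinically significant changes. The rule covers ALT, AST, GGT and "alkaline phosphatase with abnormal change defined as ratio to baseline" at 5 or more, and "total bilirubin with abnormal change defined as ratio to baseline" at 2 or more. Baseline is the last value, scheduled or not, before the first dose.

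**Which values enter (SAP 6.1).** Within a visit window, "If both scheduled and unscheduled visit data are available, the scheduled visit data will be used for analysis". An unscheduled value is used only if the window holds no scheduled one; baseline is the exception.

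**Monitoring rule (Protocol 6.5).** Repeat testing and a physical examination within 48 to 72 hours follow an "increase in AST, ALT or total bilirubin (TB) greater than 2 times their baseline values (mean of Screening & Visit 1"). On the repeat result: "Should these levels continue to be elevated, the drug should be discontinued". A further rule reads: "Subjects should be discontinued for persistent (> 1 month) increases of AST and ALT and/or TB > 2 times baseline". Rises above baseline with listed symptoms or eosinophilia also lead to stopping, with no multiple required.

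**What the protocol promises.** Protocol 11.3.1.2 commits to summarising significantly abnormal laboratory changes by treatment group. It fixes no multiple. SAP section 8, which lists departures from the protocol, does not discuss the 5-fold cut.

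**The concern.** The SAP's bilirubin cut uses the same multiple as protocol 6.5, but its ALT/AST cut is two and a half times higher (5 / 2), and no reason is given. Subjects can be retested, and in some cases taken off drug, for a transaminase rise that the abnormality table does not count.

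The trial's stated objective is the preliminary safety and efficacy of three doses against placebo in a liver disease. If one dose produced an excess of 2- to 5-fold rises, a by-arm count of subjects would show it most directly. As planned, a reader would have to rebuild that count from listings.

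**Working it through.** The plan gives no numerical figure to reproduce here, so the check sets the two rules side by side.

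**1. Thresholds.** Protocol: value > 2 × B_P, where B_P = (Screening + Visit 1) / 2. SAP: value ≥ 5 × B_S, where B_S is the last pre-dose value. If both pre-dose values equal B, the uncounted band is > 2B to < 5B.

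| Baseline B | Protocol acts above | SAP counts from |
|---|---|---|
| 60 U/L (assumed) | 2 × 60 = 120 | 5 × 60 = 300 |
| 1 × ULN | 2 × ULN | 5 × ULN |
| 2 × ULN | 4 × ULN | 10 × ULN |
| 5 × ULN (Screening eligibility limit) | 10 × ULN | 25 × ULN |

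The documents give no baseline ALT or AST distribution. The last row is the extreme that eligibility allows, not a typical subject.

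**2. Baseline definition.** Illustrative values with a mean of 60, so the protocol trigger is above 120 in both cases:
- Screening 80, Visit 1 40: SAP counts from 5 × 40 = 200.
- Screening 40, Visit 1 80: SAP counts from 5 × 80 = 400.

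The same difference affects bilirubin. On the same two patterns in arbitrary units, the SAP's 2-fold cut is 80 or 160, against a protocol trigger above 120. The multiples agree, but the rules do not fully coincide.

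**3. Repeat values.** Take a scheduled Day 90 value that triggers a repeat on Day 93. In SAP 6.1 the Month 3 window for a test measured at all visits is Days 76 to 135, so the repeat falls in the same window and gives way to the scheduled value. The triggering value is kept. What is lost is whether the repeat was higher, lower or still elevated.

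**4. Other planned outputs.**
- Descriptive statistics, including the 75th percentile and maximum (SAP 7.1, 7.9.2), mean-change plots (7.9.2) and ANCOVA against placebo (7.8.4) describe distributions. None counts subjects above 2 times baseline.
- Shift tables (7.8.4, 7.9.2) show movement in or out of range. A 2- to 5-fold rise in a subject already above range does not register.
- Adverse event tables (7.9.1) include events leading to discontinuation or interruption, but report terms, not multiples. Under Protocol 9.1.1 an abnormality that leads only to a repeat test need not be an adverse event.

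**5. Possible size, by assumption only.** Let the ratio to baseline be log-normal with median 1 and log-SD s. The share of rises above 2 that stay below 5 is 1 − P(ratio ≥ 5) / P(ratio > 2):
- s = 0.4: 1 − 0.000029 / 0.04156 = 99.9%.
- s = 1.0: 1 − 0.05376 / 0.24411 = 78%.

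With median 0.82 the range is 99.98% to 81%. The documents give no value for s, so these figures show only that the band could hold most rises above 2 times.

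**The case against.** The strongest reply is that the two rules serve different purposes. Protocol 6.5 is a sensitive trigger for monitoring individuals; SAP 7.9.2 defines a reporting category. The protocol promises a summary without fixing a multiple, so the SAP does not breach it. That stands: this is a gap in reporting, not a contradiction.

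Four stronger readings are tempting, and the documents do not support them.

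- *That this is the only by-arm evidence on liver injury.* It is not: the outputs in step 4 of the working are all by arm, and SAP 7.9.6 adds adjudicated liver events.
- *That discontinuations would go unseen.* A rise that leads to stopping drug should reach the adverse event tables if reported as such, and SAP 7.2 tabulates reasons for stopping. Protocol 6.5 can also require more than a repeat test, so many rises may qualify as adverse events. This narrows the gap but still gives no count by multiple of baseline.
- *That the 5-fold table will be nearly empty because subjects are stopped first.* In subjects without the listed symptoms or eosinophilia, stopping depends on the rise staying elevated or persisting, and rechallenge is allowed. Scheduled visits are 90 days apart after Month 3, so a first detected value can already be 5 times or more.
- *That the override discards the peaks.* Nothing shows that repeats are higher, and protocol 6.5 provides for levels that fall.

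Local-laboratory results are not entered in the database (Protocol 7.4), so no table can recover repeats done locally.

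**Conclusion.** The point holds as a limited reporting gap. For ALT and AST, no planned table counts subjects by arm above 2 and below 5 times baseline, although protocol 6.5 acts there. Rises of 5 times or more are counted when the tabulated value reaches that level on the SAP's baseline. Bilirubin is already counted at 2 times, apart from the different baseline and ≥ in place of >. The difference in baseline and the priority for scheduled values widen the mismatch but are secondary.

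The number of subjects affected cannot be derived from the documents: the 60 U/L baseline and the log-normal spread are assumptions. The conclusion also takes the protocol trigger to mean a value above twice baseline. Read instead as an increment of twice baseline, the trigger would be above 3 times (B + 2B), and the uncounted band would be 3 to 5 times. The primary efficacy inference is unaffected. The change is worth making because it is cheap and serves the trial's safety objective directly.

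**What to change.** In SAP 7.9.2, before unblinding for the final analysis, keep the 5-fold row and add, by arm:

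- the number and percentage of subjects with any on-treatment central-laboratory value, scheduled or unscheduled, above 2 times the protocol 6.5 baseline, separately for ALT, AST and total bilirubin;
- the number and percentage with ALT or AST above 2 times together with bilirubin above 2 times, with the SAP stating which samples count as together.

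On-treatment can follow the safety set's existing limit of 14 days after the last dose. State that the SAP 6.1 priority for scheduled values does not apply to these rows, give the reason for the 5-fold cut, and footnote that local-laboratory repeats are absent.

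The cost is a few descriptive rows and one derived baseline, from central data already collected. There is no new test, and no change to monitoring or stopping rules.
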